8.2 Other Assessments

8.2.1 Outcome Research Assessments

Quality of life data will be obtained using the SGART, AE-QoL questionnaire, EQ-5D-5L questionnaire, WPAI:GH questionnaire (to be completed by the subject in this order), and IGART. Quality of life data will be captured electronically using a provisioned electronic Clinical Outcome Assessment (eCOA) solution.

The age considerations for these assessments are:

- EQ-5D-5L: all ages
- SGART: all ages
- IGART: all ages
- WPAI: ≥ 16 years
- AE-QoL: ≥ 18 years

8.2.1.1 Angioedema Quality of Life Questionnaire

The AE-QoL questionnaire is an instrument to assess quality of life impairment in subjects with recurrent angioedema attacks [Weller et al, 2012].

The AE-QoL is a questionnaire that covers 4 dimensions (functioning, fatigue / mood, fear / shame, and nutrition), and consists of 17 questions with 5 levels of response (never, rarely, occasionally, often, and very often). A linear transformation of raw scores results in a range of possible total scores from 0 (minimum) to 100 (maximum).

The AE-QoL will be completed using a provisioned eCOA solution.

Further details will be provided in the statistical analysis plan (SAP).

8.2.1.2 EQ-5D-5L

The EQ-5D-5L is a standardized measure of health status that provides a simple, generic measure of health for clinical and economic appraisal. The questionnaire, which is designed for self-completion by respondents, is applicable to a wide range of health conditions and treatments [EuroQol Group, 1990].

The EQ-5D-5L consists of 2 parts:

- A descriptive profile, comprising the following 5 dimensions: mobility, self-care, usual activities, pain / discomfort, and anxiety / depression. Respondents rate each dimension based on 5 levels of severity (ie, no problems, slight problems, moderate problems, severe problems, extreme problems).
- A vertical, visual analog scale, on which the respondent rates their overall health from 'Best imaginable health state' to 'Worst imaginable health state.'

Subjects are to complete the EQ-5D-5L using a provisioned eCOA solution. Additional details will be provided in the SAP.

8.2.1.3 Work Productivity and Activity Impairment Questionnaire: General Health

The WPAI:GH questionnaire is an instrument to measure impairments in both paid and unpaid work [Reilly et al, 1993].

The WPAI:GH measures absenteeism, presenteeism, as well as impairments in unpaid activity because of health problems during the 7 days before administration of the questionnaire. It has been validated to quantify work impairments for numerous diseases. The WPAI:GH has been used to compare work impairments between treatment groups in clinical studies or between subjects with different disease severity levels.

WPAI:GH outcomes are expressed as impairment percentages, with higher numbers indicating greater impairment and less productivity (ie, worse outcomes).

The WPAI:GH will be completed using a provisioned eCOA solution.

Further details will be provided in the SAP.

8.2.1.4 Subject's Global Assessment of Response to Therapy

The overall response to treatment with the investigational product will be self-assessed by the subject using the SGART.

The SGART will measure the subject's overall treatment response to the investigational product using the following ratings:

- (0) none – worse or no response at all, not acceptable
- (1) poor – very little response, not acceptable
- (2) fair – some response, acceptable but could be better
- (3) good – good response, acceptable
- (4) excellent – excellent response, as good as can be imagined

The SGART will require subjects to rate themselves using the following direction (or an appropriate translation, as applicable): "Considering all of the ways HAE affects you, please

rate your response to the study medication you were given to prevent HAE attacks during this Treatment Period.”

The SGART will be completed using a provisioned eCOA solution.

Further details will be provided in the SAP.

8.2.1.5 Investigator's Global Assessment of Response to Therapy

The overall response to treatment with the investigational product will be assessed by the investigator using the IGART.

The IGART will measure the subject's overall treatment response to the investigational product using the following ratings:

- (0) none – worse or no response at all, not acceptable
- (1) poor – very little response, not acceptable
- (2) fair – some response, acceptable but could be better
- (3) good – good response, acceptable
- (4) excellent – excellent response, as good as can be imagined

The IGART will require the investigator to rate subjects using the following direction (or an appropriate translation, as applicable): “Considering all of the ways HAE affects your patient, please rate your patient's response to the study medication provided to prevent HAE attacks during this Treatment Period.” Whenever possible, the same investigator will perform the IGART for each subject throughout the study.

The IGART will be completed in the eCRF.

Further details will be provided in the SAP.

8.2.2 Electronic Diary and Electronic Clinical Outcome Assessments

The study will employ 3rd-party provisioned eCOA solution to capture both patient-reported outcome (PRO) measures and eDiary information.

Patient-reported outcome assessments will be completed by subjects using the eCOA solution via a provisioned electronic device (eg, tablet) provided at the study site. eDiary entries will also be completed via a provisioned electronic device (eg, handheld) and are to be entered by

the subject while at home. Subjects will be fully trained by the site staff in the use of the eDiary and tablet. Refer to [Section 8.1.3](#) for eDiary content.

The following assessments will be completed by the subject using the eCOA solution at the study site:

- SGART
- AE-QoL
- EQ-5D-5L
- WPAI:GH

A web portal will provide site staff with on-demand, role-based access to all PRO data and eDiary data.

8.3 Blood Samples

During the study, blood will be taken from each subject for laboratory safety assessments and PK / PD evaluations. Detailed information on the volume of blood to be sampled for each assessment will be available in the laboratory manual. Repeat or unscheduled blood samples may be taken for safety reasons or for technical issues with the samples.

Information on the volume of blood to be collected for each visit will be available in the informed consent form (ICF).

Refer to the laboratory manual for details about the volume, collection, storage, handling and processing of blood samples.

8.4 Retention of Samples

Refer to the laboratory manual for further details about the storage and destruction of retention samples.

8.4.1 Retention Sample for HAE Biomarkers

Blood samples for potential future assessment of HAE biomarkers will be obtained during the Treatment Period at all visits, including the End of Treatment Visit (Day 182), as well as at the Follow-up Visit. These samples will be stored for potential testing of HAE biomarkers and will be destroyed within 5 years after completion of the study.

8.5 Prior and Concomitant Therapies

All medications and therapies that have been administered to a subject within 6 months before signing informed consent are regarded as prior medications and therapies and must be documented as such in the eCRF.

All drugs and / or procedures currently being administered to a subject at the time of signing informed consent, and which continue to be taken in addition to investigational product during the study, are regarded as concomitant therapies. All concomitant therapies will be recorded in the subject's eCRF.

Both pharmacological (eg, prescription and over-the-counter medications, and herbal and vitamin supplements) and nonpharmacological (eg, any surgical or diagnostic procedures) will be reported.

8.6 Electrocardiograms

A standard 12-lead electrocardiogram (ECG) will be performed (single reading) according to the Schedule of Assessments ([Schedule of Assessments: Treatment Period](#)). The date and time of each ECG will be recorded in the source documents and the eCRF. The ECG will be sent to a central vendor for reading and assessment.

8.7 Visit Schedule

8.7.1 Assessment Time Windows

The timing and frequency of the study visits are described in the [Schedule of Assessments: Screening and Run-in Period \(All Subjects\)](#) and [Schedule of Assessments: Treatment Period](#). Time windows for all assessments are detailed in [Table 6](#).

Table 6 Time Windows for Assessments

Visit / Procedure	Time window (relative to scheduled visit / procedure)
Screening	Not applicable
Run-in Period: Visit Days 15, 30, 45, and 60	± 4 days
Treatment Period: Visit Days 31, 61, 91, 121, 151, 182	± 4 days
Follow-up: Visit Day 242	- 14 days
Vital signs, physical examination, and pregnancy test	Preinjection on same day

8.7.2 Screening Visit

All subjects (or the subject's authorized representative) must provide written informed consent before any study-specific assessments or procedures are performed. Written informed consent is not required for assessments or procedures performed according to standard of care (eg, for diagnosis or treatment); results from such assessments may be used in the determination of study eligibility. Subjects will be allowed to be rescreened (see [Section 4.2](#)).

A screening examination should be performed within 30 days before the start of the Run-in Period.

The following procedures will be conducted and documented at the Screening Visit:

- Obtain written informed consent and register the subject via the IRT.
- Review inclusion and exclusion criteria.
- Obtain relevant medical history including overall health for at least the 6 months before the Screening Visit, HAE history before Screening, and contraception method (for females of childbearing potential only).
- Record subject demographics.
- Collect urine for pregnancy test (for sexually active women of childbearing potential).
- Perform physical examination.
- Record vital signs, including height and body weight.
- Collect urine for urinalysis.
- Collect blood for:

- Hematology
- Biochemistry
- Coagulation
- C1-INH functional activity and antigen, and C4 antigen concentration for confirmation of historical laboratory values contained in the subject's medical record.
- Develop an individual acute action plan, including assessment of subject's ability to manage HAE attacks and confirmation of subject's access to on-demand HAE medication to treat HAE attacks.
- Perform eDiary training
- Record prior and concomitant medications and therapies (type, dose, route, date, and time) in the last 6 months.
- Begin to monitor AEs.

Re-screening: If a potential subject is not eligible for entry into the Run-in Period within 30 days after providing informed consent, then the subjects may re-consent and may be screened again (for a maximum of 2 Screening Periods per subject) after consultation with CSL. In the event that a potential subject is screened twice, all Screening assessments must be repeated during the second Screening Period. If the subject is not eligible for the study (ie, the subject is a Screen Failure), all eligibility criteria that are not met must be recorded in IRT.

8.7.3 Run-in Period

8.7.3.1 Run-in Period: Visit Day 1

Subjects who complete all Screening assessments and who fulfill the eligibility criteria (ie, eligible subjects) will be enrolled into the study. The first day of the Run-in Period and Screening may occur on the same day. If the Run-in Period begins after Screening, then the first day of the Run-in Period begins with a telephone contact.

The following procedures will be conducted:

- Re-confirm subject eligibility.
- Record start of Run-in Period in IRT.
- Telephone contact for all subjects (not applicable if performed on same day as Screening Visit).

- eDiary training if initial training was conducted 30 days before Run-in Period.
- Open subject access to eDiary and review diary instructions with subject.
- eDiary completion by subject.
- Confirm access to on-demand HAE medication.
- Record prior and concomitant medications and therapies (type, dose, route, date, and time).
- Record AEs.

8.7.3.2 Run-in Period: Visit Days 15, 30, and 45 ± 4 days

The following procedures will be conducted at Visit Days 15, 30, and 45 during the Run-in Period:

- Telephone contact for all subjects.
- eDiary completion by subject.
- Review of eDiary data.
- Assess / document HAE attacks.
- Confirm access to on-demand HAE medication.
- Record concomitant medications and therapies (type, dose, route, date, and time).
- Record AEs.

Subjects must participate in the Run-in Period for at least 1 month. Subjects may exit the Run-in Period and enter the Treatment Period when they have met the criteria specified in protocol (Section 4.1). Specifically, subjects must have experienced an average of 1 HAE attack per month during the 2-month Run-in Period (ie, for a minimum of 2 HAE attacks if the subject enters the Treatment Period with 2 months from Day 1 of Run-in).

8.7.3.3 Run-in Period: Day 60 ± 4 days

The following procedures will be conducted at Visit Day 60 during the Run-in Period:

- Telephone contact for all subjects.
- eDiary completion by subject.

- Review of eDiary data.
- Close eDiary access (only applicable for subjects not eligible to enter the Treatment Period).
- Confirm access to on-demand HAE medication.
- Record concomitant medications and therapies (type, dose, route, date, and time).
- Record AEs.

Subjects should enter the Treatment Period no later than 15 days after the Day 60 telephone contact. If a subject is unable to enter the Treatment Period within the 15 days after the Day 60 telephone contact, then CSL approval is required for the subject to enter the Treatment Period. The Day 60 telephone contact will conclude the Run-in Period for a subject who has entered the Run-in Period and is subsequently not eligible to be assigned to treatment with investigational product in the Treatment Period.

Subjects who enter the Run-in Period but are not eligible to enter the Treatment Period will be considered Run-in failures. If a subject is not eligible to enter the Treatment Period, the primary reason for Run-in failure must be documented. These subjects may not be rescreened.

8.7.4 Treatment Period

8.7.4.1 Treatment Period: Visit Day 1

Subjects who complete all screening assessments, fulfill the eligibility criteria (ie, eligible subjects), and meet the Treatment Period entry criteria ([Section 4.1.3](#)) will be randomized to investigational product. The following procedures are to be conducted and documented:

- Confirm eligibility for Treatment Period.
- Randomization and assignment of investigational product via IRT.
- Collect urine for pregnancy test (for sexually active women of childbearing potential).
- Perform physical examination.
- Record vital signs and body weight.

- Perform ECG (ECG may be performed during the Run-in Period as an alternative).
- Urine collection for urinalysis*
- Collection of blood to assess:
 - Hematology.*
 - Biochemistry.*
 - Coagulation.*
 - HAE biomarkers (retention sample) (adults only).
 - PK / PD.
 - Immunogenicity.
- Record concomitant medications and therapies (type, dose, route, date, and time).
- Record AEs.
- PRO / eCOA tablet training.
- Subject to complete:
 - AE-QoL (subjects \geq 18 years).
 - EQ-5D-5L.
 - WPAI:GH (subjects \geq 16 years).
- eDiary completion by subject.
- Review eDiary data, including investigator assessment of HAE symptoms and documentation of HAE attacks.
- Confirm access to on-demand HAE medication.
- Obtain investigational product kit assignment in IRT.
- Subcutaneous administration of investigational product loading dose by investigator or delegate (after completion of pregnancy test, physical examination, vital signs, and collection of blood samples).
- Accountability of investigational product.

*Assessment may be omitted if Screening / Run-in Period assessments occurred within the previous 3 months.

8.7.4.2 Treatment Period: Visit Days 31, 61, 121, and 151 (\pm 4 days)

The following procedures will be conducted at the Day 61 and Day 151 (\pm 4 days) site visits:

- Collect urine for pregnancy test (for women of childbearing potential and sexually active).
- Perform physical examination.
- Record vital signs and body weight.
- Collection of blood to assess:
 - PK / PD.
 - HAE biomarkers (retention sample) (adults only).
- Record concomitant medications and therapies (type, dose, route, date, and time).
- Record AEs.
- Subject to complete:
 - AE-QoL (subjects \geq 18 years).
 - WPAI:GH (subjects \geq 16 years).
- eDiary completion by subject.
- Review eDiary data, including investigator assessment of HAE symptoms and documentation of HAE attacks.
- Confirm access to on-demand HAE medication.
- Obtain investigational product kit assignment in IRT.
- Subcutaneous administration of investigational product by subject under supervision (after completion of pregnancy test, physical examination, vital signs, and blood sample collection).
- Accountability of investigational product.
- Offer subject option to enroll in Study CSL312_3002 (Day 151 only).

8.7.4.3 Treatment Period: Visit Day 91 \pm 4 days

The following procedures will be conducted at the Day 91 \pm 4 days site visit:

- Collect urine for pregnancy test (for women of childbearing potential and sexually active).
- Perform physical examination.
- Record vital signs and body weight.
- Urine collection for urinalysis.
- Collection of blood to assess:
 - Hematology.
 - Biochemistry.
 - Coagulation.
 - PK / PD.
 - HAE biomarkers (retention sample) (adults).
 - Immunogenicity.
- Document concomitant medications and therapies (type, dose, route, date, and time).
- Record AEs.
- Subject to complete:
 - SGART.
 - AE-QoL (subjects \geq 18 years).
 - EQ-5D-5L.
 - WPAI:GH (subjects \geq 16 years).
- IGART.
- eDiary completion by subject.
- Review eDiary data, including investigator assessment of HAE symptoms and documentation of HAE attacks.
- Confirm access to on-demand HAE medication.
- Obtain investigational product kit assignment in IRT.

- Subcutaneous administration of investigational product by subject under supervision (after completion of pregnancy test, physical examination, vital signs, and blood sample collection).
- Accountability of investigational product.

8.7.4.4 End of Treatment Period: Visit Day 182 ± 4 days

The following procedures will be conducted at the Day 182 ± 4 days site visit:

- Collect urine for pregnancy test (for sexually active women of childbearing potential).
- Perform physical examination.
- Record vital signs and body weight.
- Perform ECG.
- Urine collection for urinalysis.
- Collection of blood to assess:
 - Hematology.
 - Biochemistry.
 - Coagulation.
 - HAE biomarkers (retention sample) (adults only).
 - PK / PD.
 - Immunogenicity.
- Document concomitant medications and therapies (type, dose, route, date, and time).
- Record AEs.
- Subject to complete:
 - SGART.
 - AE-QoL (subjects ≥ 18 years).
 - EQ-5D-5L.
 - WPAI:GH (subjects ≥ 16 years).
- IGART.
- eDiary completion by subject.
- Review eDiary data, including investigator assessment of HAE symptoms and documentation of HAE attacks.
- Device deactivation (eg, eDiary and Tablet) (for subjects entering Study CSL312_3002).

- Confirm access to on-demand HAE medication.

8.7.5 Follow-up Telephone Contact or Final Visit

Follow-up is only applicable to subjects not entering the phase 3b Study CSL312_3002. This visit may be waived in place of a telephone contact. If the visit is to be conducted in person, the following procedures will be performed by the investigator or delegate at Follow-up: Visit Day 242 (- 14) days; 3 months after the last investigational product administration or upon a subject's early termination from the study:

- Collection of blood to assess:
 - HAE biomarkers (retention sample) (adults only).
 - PK / PD.
- Document concomitant medications and therapies (type, dose, route, date, and time).
- Record AEs.
- Review eDiary data, including investigator assessment of HAE symptoms and documentation of HAE attacks.
- Device deactivation (eg, eDiary and Tablet) (for subjects not entering Study CSL312_3002).

8.7.6 End of Study

The scheduled end of study participation for an individual subject occurs with completion of Day 242 (-14 days) or upon entry into the phase 3b study at Day 182, after which no further study-related procedures will be performed.

9 Adverse Events

9.1 Definitions

9.1.1 Adverse Event

As per the ICH Topic E2A (Clinical Safety Data Management: Definitions and Standards for Expedited Reporting), an AE is any untoward medical occurrence in a patient or clinical investigation subject administered a pharmaceutical product and which does not necessarily have a causal relationship with this treatment. An AE can, therefore, be any unfavorable and unintended sign (including an abnormal, clinically significant laboratory finding), symptom,

or disease temporally associated with the use of a medicinal (investigational) product, whether or not considered related to the medicinal (investigational) product.

The period of observation for AEs extends from the time the subject gives informed consent until the end of study (see [Section 9.4](#) for further details).

Adverse events may include:

- Exacerbation (ie, an increase in the frequency or severity) of a pre-existing condition. Illness present before study entry should be recorded in the medical history section of the eCRF and only be reported as an AE if there is an increase in the frequency or severity of the condition during the study.
- A clinical event occurring after consent but before investigational product administration.
- Intercurrent illnesses with an onset after administration of investigational product.

Adverse events do not include:

- Events identified at Screening that meet exclusion criteria.
- Medical or surgical procedures (the condition that leads to the procedure is the AE).
- Situations where an untoward medical occurrence has not taken place. For example:
 - Planned hospitalizations due to pre-existing conditions, which have not worsened.
 - Hospitalizations that occur for procedures not due to an AE (eg, cosmetic surgery).
 - Hospitalizations for a diagnostic procedure where the hospital stay is less than 24 hours in duration or for normal management procedures (eg, chemotherapy).
 - Overdose of investigational product or any concomitant therapy that does not result in any adverse signs or symptoms.

For laboratory safety parameters, any instances of absolute values being outside the reference range or changes at any visit after study start that are considered by the investigator as clinically significant must be recorded in the eCRF as AEs. In addition, at the investigator's discretion, any changes or trends over time in laboratory parameters can be recorded in the eCRF as AEs if such changes or trends are considered to be clinically relevant, even if the absolute values are within the reference range.

Laboratory findings do not need to be reported as AEs in the following cases:

- Laboratory parameters already beyond the reference range at Screening, unless a further increase / decrease can be considered an exacerbation of a pre-existing condition.

- Abnormal laboratory parameters caused by mechanical or physical influences on the blood sample (eg, in vitro hemolysis) and flagged as such by the laboratory in the laboratory report.
- Abnormal parameters that are obviously biologically implausible (eg, values that are incompatible with life or outside the measuring range).
- An abnormal laboratory value that cannot be confirmed after repeat analysis, preferably in the same laboratory (ie, the previous result could be marked as not valid and should not necessarily be reported as an AE).

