Details related to the collection, preparation, and transfer of blood and urine samples for laboratory assessments will be provided in the Laboratory Manual.

Refer to [Section 9.1.1](#) for assessment of abnormal laboratory values. Tests resulting in abnormal laboratory values during the study period that have been classified by the investigator as clinically significant should be followed up after receiving the laboratory report and may include an unscheduled repeat safety sampling at the discretion of the investigator.

Vital Signs

Blood pressure and heart rate will be measured with the subject in a supine or seated position after resting for at least 5 minutes. Body temperature will be measured either sublingually or tympanically, and the method of measurement should be consistent throughout the study for a given subject.

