1.	The time-normalized number of moderate and / or severe HAE attacks	The time-normalized number (per month and annualized) of moderate and / or severe HAE attacks in subjects treated once a month with either CSL312 (Active Arm) or placebo (Placebo Arm) during the period from Day 1 through Day 182 (6 months), as well as for the first 3-month time period and for the second 3-month time period of the Active and Placebo arm.
1.	Time-normalized number of HAE attacks at various time points during the treatment period	
The time-normalized number of HAE attacks (per month and annualized) in subjects treated once monthly with either CSL312 (Active Arm) or placebo (Placebo Arm) during the first 3-month time period and the second 3-month time period of CSL312 (Active Arm) and placebo (Placebo Arm).
 
The percentage reduction will be calculated for the time-normalized number of HAE attacks between the Active Arm and the Placebo Arm for the 6-month treatment period, as well as for the first 3 months and the second 3 months of the treatment period.

1.	CCI [REDACTED] [REDACTED]	Comparison of the distribution of responses to therapy between CSL312 and placebo at the end of the Treatment Period at Day 182 based on the proportions of subjects with a "excellent, good, fair, poor or none" response to therapy.
Safety Endpoints		
2.	
 • AEs • AESIs • SAEs • CSL312 induced anti-CSL312 antibodies • Clinically significant abnormalities in laboratory assessments (ie, laboratory abnormalities reported as AEs). 	The number and percentage of subjects experiencing the specified safety events on treatment with CSL312 or placebo during the entire Treatment Period until Follow-up or Final Visit.

CCI

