8.2.5 Multiple Assessments

All data will be reported according to the nominal visit date for which it was reported (that is, no visit windows will be applied during data set creation to re-assign assessments to other visits or time points based on such windows).

If a laboratory sample was repeated due to technical problems the results from the valid sample(s) for this visit will be used in the analysis. If a laboratory sample was repeated as safety follow-up to monitor abnormal values of the initial sample, the initial sample (revealing the abnormal values) of this visit will be used in the analysis.

[figure not shown]
Data from all assessments (scheduled and unscheduled), including multiple assessments, will be included in listings.

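### Protocol 9.1.1 treats a laboratory result outside the assay's measuring range as an example of biological implausibility, so a true extreme value may go unreported as an AE and be missed by the AE-based laboratory endpoint

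*Protocol*

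**What the plan says.** Protocol section 9.1.1 starts from a mandatory rule. Laboratory values outside the reference range, or changes, "that are considered by the investigator as clinically significant must be recorded in the eCRF as AEs". A list of exemptions follows under the words "Laboratory findings do not need to be reported as AEs in the following cases". Two of its items matter here:

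- "Abnormal parameters that are obviously biologically implausible (eg, values that are incompatible with life or outside the measuring range", where the measuring-range case is one of two examples of implausibility.
- "An abnormal laboratory value that cannot be confirmed after repeat analysis, preferably in the same laboratory", with the added remark that "the previous result could be marked as not valid and should not necessarily be reported as an AE".

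The secondary safety endpoint on laboratory assessments is defined, in Protocol section 2.2.2 and SAP section 4.1 alike, as "laboratory abnormalities reported as AEs". SAP section 11.3 also counts subjects with clinically significant laboratory findings, but only those related to a treatment-emergent AE.

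Two further provisions deal with repeats. Protocol section 8.1.1 says that follow-up of a value already classified as clinically significant "may include an unscheduled repeat safety sampling at the discretion of the investigator". SAP section 8.2.5 says that after a technical repeat the valid sample is used, whereas after a repeat for safety follow-up "the initial sample (revealing the abnormal values) of this visit will be used in the analysis".

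**The concern.** The measuring-range example puts two different things in one class. A value incompatible with life is implausible because of biology. A value outside the measuring range is one that the assay could not quantify. The second kind can be a true result at the extreme end, for instance a D-dimer or a liver enzyme (both in the Protocol's Table 4) returned only as greater than the upper limit. This is a general property of assays. The documents neither state it nor contradict it.

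At stake is the completeness of one secondary safety endpoint. That endpoint takes its numerator from AE reporting, so an exemption from AE reporting is also an exemption from the endpoint. If the rule is applied as written, some of the most abnormal true values could be absent from the count.

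**Working it through.** No formula applies and the plan states no figure to reproduce. The check is to set the provisions side by side and follow one result through them.

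**Step 1: the two rules in Protocol 9.1.1.** Suppose a result is reported as above the assay's upper limit and the investigator considers it clinically significant. The opening rule says it must be recorded. The exemption list gives a result outside the measuring range as an example of a finding that need not be reported. Both rules fit the same result, and the section gives no order of precedence.

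**Step 2: from AE reporting to the endpoint.**

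| Output | Does it depend on an AE report? | Unreported off-range value |
|---|---|---|
| Laboratory safety endpoint (Protocol 2.2.2, SAP 4.1) | Yes, by definition | Missing |
| Count of clinically significant findings (SAP 11.3) | Yes, tied to a treatment-emergent AE | Missing |
| Listing of all laboratory results (SAP 11.3) | No | Kept |
| By-subject listing of abnormal results (SAP 11.3) | No | Kept |

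The second count is therefore no backstop for the first. The listings are a backstop, but they are not the endpoint. The readable SAP does not say how an off-range safety result enters the visit-level descriptive statistics. Parts of its section 8.2 are blacked out, so nothing here rests on that.

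**Step 3: the repeat clause.** Protocol 9.1.1 does not say whether the repeat analysis uses the same specimen or a new one.

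- Same specimen: the clause concerns the validity of a measurement and agrees with the technical-repeat rule in SAP 8.2.5.
- New specimen: a normal later value could be used to mark an earlier true abnormality as not valid, while SAP 8.2.5 would keep that earlier value in the laboratory summaries.

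The allowance for a different laboratory, and the separate exemption for sample faults flagged by the laboratory, leave the second reading open. The separate term for a new draw in Protocol 8.1.1 favours the first.

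**Step 4: scale.** SAP 4.5 works with 36 CSL312 and 24 placebo subjects. One subject is 1/36 = 2.8% of the active arm or 1/24 = 4.2% of the placebo arm. This is the weight of a single subject, not an estimate of loss. The documents give no assay ranges, no expected frequency of off-range or unconfirmed results, and no expected rate of laboratory AEs.

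**The case against.** The best defence is that the exemption is bounded by its own words. The value must be obviously implausible, and the measuring range is only an example. A sensible investigator would not call a high but credible result implausible, and would record it under the mandatory rule. The list is also permissive: nothing in it forbids or discourages reporting. This stands as a limit on the claim. It does not remove the fault, because the text names off-range results as an instance of the exempt class and a site that follows the example is compliant.

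Three stronger readings might be inferred, and the documents do not support them.

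- *Extreme and transient abnormalities drop out of the endpoint.* The list makes reporting optional, so the most that can be said is that extreme values may go unreported. Transient values come in only if repeat analysis includes a new specimen, which the Protocol leaves open. The new draw in Protocol 8.1.1 follows values already judged clinically significant, which the opening rule of 9.1.1 says must be recorded.
- *The Protocol and SAP 8.2.5 contradict each other.* This depends on the same open reading. In addition, SAP 8.2.5 selects values for analysis by visit and does not govern AE reporting.
- *The endpoint is biased exactly where the drug's named risks would show.* Thromboembolic, bleeding and severe hypersensitivity events are captured as AEs of special interest (Protocol 9.1.3), and anti-CSL312 antibodies are a separate endpoint. The expected laboratory effect, prolonged aPTT, is withheld from sites (Protocol 6.3.1), so this list is not what keeps it out of AE reports.

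**Conclusion.** The measuring-range example is wrong as written. It confuses an assay limit with biological implausibility and sits unreconciled beside the rule that clinically significant values must be recorded. A true, very abnormal result beyond the assay limits may therefore go unreported as an AE and be missing from both AE-based laboratory counts, although it remains in the listings. The conclusion assumes only that results beyond an assay limit can be genuine and that some site might follow the example as written.

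The size cannot be estimated. A reader could assume one to three affected CSL312 subjects and conclude that a true 2.8% to 8.3% (1/36 to 3/36) would appear as zero. That count has no source in the documents. It also requires every such subject to go unreported and none to have another reported laboratory AE.

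The undefined repeat analysis is a lesser matter of clarity. Neither point touches the primary analysis, the sample size or the hierarchical tests.

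**What to change.** In Protocol 9.1.1, delete the measuring-range example from the item on implausible values. Add that a result above or below the measuring range is assessed for clinical significance like any other abnormal value, and is recorded as an AE if clinically significant.

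As a secondary clarification, limit the item on unconfirmed values to re-analysis of the same specimen or a documented technical fault, in line with the distinction in SAP 8.2.5. A normal result in a later specimen would then not invalidate an earlier abnormal one.

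The cost is a wording change in the Protocol and in any matching eCRF guidance, and possibly a few more laboratory AEs in both arms. The endpoint definition need not change.
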